7.7.4 Substudy 4: Atrial fibrillation/flutter

Substudy 4A

A cohort study estimating the incidence of A-fib/flu in the general population will be performed. The cohort of individuals with A-fib/flu and the distribution of the population by age, year, and country will be used to derive estimates in the general population. The number of individuals in the general population on 01 January of each year will be obtained from the NORDCAN database and used as an estimate of the number of person years at risk assuming each person in the population on 01 January of each year contributes one person year at risk [Association of Nordic Cancer Registries 2009]. The IRs of A-fib/flu will be shown for the

total population and for each country, sex, and age. The confidence interval of IRs is calculated as outlined above under Substudy 2A.

Substudy 4B

A cohort study among ever-DL users analyzing the association between exposed and unexposed time (as defined in Substudy 2B) and first A-fib/flu diagnosis will be performed for the total population and stratified by age. A person who has redeemed at least one prescription of DL is included in the cohort and enters the cohort at the date of first prescription redemption. Study individuals are followed until occurrence of A-fib/flu; 31 December 2015; emigration or death, whichever comes first. The association between exposure to DL use and first A-fib/flu will be evaluated using Poisson regression of the IR of first A-fib/flu, and the measure of effect is the IRR. A person with prescription redemption of DL in Norway and Sweden within the first 6 months after establishment of the prescriptions registers will not be included in order to account for truncation bias. In addition we exclude persons with DL prescription redemptions within 6 months after immigrating to Denmark, Finland, Norway, or Sweden. The analyses will be adjusted for confounders identified from the DAG (i.e., country, age, sex, calendar years, seasonality, severity of rhinitis, asthmatic status, and chronic urticaria status) (Table 4). We will evaluate whether age can be included as a continuous variable by examining the assumption of linearity. Alternatively, age will be included as a categorical variable.

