7.2.2 Exclusion criteria

Substudy 2A

- Individuals with a diagnosis of seizure, epilepsy, or prescriptions of antiepileptic medicine before entering the study period, as they have prevalent disease.
- Individuals with a diagnosis of malignant brain tumor or head trauma before the first seizure, as they are at high risk of seizures due to causes other than DL use.

Substudy 2B

- Individuals with a diagnosis of seizures, epilepsy, prescriptions of antiepileptic medicine, malignant brain tumor, or head trauma before redemption of first DL prescription, as they have prevalent disease or are at high risk of seizures due to causes other than DL use.
- Individuals with a brain tumor (benign and malignant), initiation of treatment with antiepileptic medicine, or head trauma occurring after beginning of DL use will be censored at date of first occurrence, as they are at high risk of seizures due to causes other than DL use.

Substudies 3A and 4A

- Individuals with a diagnosis of SVT or A-fib/flu before entering the study period, as they have prevalent disease.
- Individuals with a diagnosis of congenital pre-excitation syndrome (e.g., Wolff Parkinson White) before entering the study period, as they are at high risk of cardiac SVT or A-fib/flu due to causes other than DL use.

Substudies 3B and 4B

- Individuals with a diagnosis of SVT or A-fib/flu before use of DL, as they have prevalent disease.
- Individuals with a diagnosis of congenital pre-excitation syndrome (e.g., Wolff Parkinson White) before use of DL, as they are at high risk of SVT or A-fib/flu due to causes other than DL.

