7.3.2 Outcomes

Three outcome variables will be used in the present study: first seizure (Substudy 2B), first SVT (Substudy 3B), and first A-fib/flu (Substudy 4B). Except where noted, the case definition of seizure excludes febrile seizure, a condition in infancy and early childhood attributed to fever. However, supplementary analysis 2 will evaluate the outcomes of febrile and non-febrile seizures in children. (The diagnosis of febrile seizure is generally not used in adults.) Information on outcome variables will be obtained from the Nordic national patient registers, including diagnostic and treatment information for patients treated at the secondary and tertiary hospital level in all four Nordic countries using International Classification of Diseases (ICD)- 10 codes. We will exclude seizure cases if they are registered with brain tumor (benign and malignant), stroke, or acute drug intoxication or overdose of drugs during the same hospitalization as the seizure. [Table 2](#) gives an overview of the outcome variables in the study. For all outcome variables, we will include the primary diagnoses from the emergency room or inpatient settings registered in the Nordic national patient registers.

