A cohort study among ever-DL users analyzing the association between exposed and unexposed time and first seizures will be performed for the total population and stratified by age. Current use (i.e., “exposed” period) will be defined for each prescription as days’ supply plus a 4 week grace period to account for intermittent use and a possible wash-out effect. Unexposed time will be defined as the period starting 26 weeks from the dispensing date of the prior DL prescription until the next DL prescription redemption, if any. A person who has redeemed at least one prescription of DL is included in the cohort and enters the cohort at the date of first prescription redemption. Study individuals are followed until occurrence of a seizure; occurrence of one of the conditions described in section 7.2.2; 31 December 2015; emigration; or death, whichever comes first. The association between exposure to DL and first seizure will be evaluated using Poisson regression of the IR of first seizure, and the measure of effect is the IRR. A person with prescription redemption of DL in Norway and Sweden within the first 6 months after establishment of the prescriptions registers will not be included in order to account for truncation bias. In addition we exclude persons with DL prescription redemptions within 6 months after immigrating to Denmark, Finland, Norway, or Sweden. The analyses will be adjusted for confounders identified from the DAG (i.e., country, age, sex, calendar year, seasonality, severity of rhinitis, asthmatic status, and chronic urticaria status) (Table 4). We will evaluate whether age can be included as a continuous variable by examining the assumption of linearity. Alternatively, age will be included as a categorical variable.

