7.7.3 Substudy 3: SVT

Substudy 3A

A cohort study estimating the incidence of SVT in the general population will be performed. The cohort of DL users, the cohort of individuals with SVT, and the distribution of the population by age, year, and country will be used to derive estimates in the general population. The number of individuals in the general population on 01 January of each year will be obtained from the NORDCAN database and used as an estimate of the number of person years at risk assuming each person in the population on 01 January of each year contributes one person year at risk [Association of Nordic Cancer Registries 2009]. The IRs of SVT will be shown for the total population and stratified by country, sex, and age. The confidence interval of IRs is calculated as outlined above under Substudy 2A.

Substudy 3B

A cohort study among ever-DL users analyzing the association between exposed and unexposed time (as defined in Substudy 2B) and first SVT will be performed for the total population and stratified by age. A person who has redeemed at least one prescription of DL is included in the cohort and enters the cohort at the date of first prescription redemption. Study individuals are followed until occurrence of a SVT; 31 December 2015; emigration; or death, whichever comes first. The association between exposure to DL use and first SVT will be evaluated using Poisson regression of the IR of first SVT, and the measure of effect is the IRR. A person with prescription redemption of DL in Norway and Sweden within the first 6 months after establishment of the prescriptions registers will not be included in order to account for truncation bias. In addition we exclude persons with DL prescription redemptions within 6 months after immigrating to Denmark, Finland, Norway, or Sweden. The analyses will be adjusted for confounders identified from the DAG (i.e., country, age, sex, calendar year, seasonality, severity of rhinitis, asthmatic status, and chronic urticaria status) (Table 4). We will evaluate whether age can be included as a continuous variable by examining the assumption of linearity. Alternatively, age will be included as a categorical variable.

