- The present study aims at studying incident outcomes occurring in the community setting. To differentiate between incident and prevalent disease, we exclude persons with registered disease before baseline. In addition, we used surrogates of prevalence (i.e., redeemed prescriptions of antiepileptic medicine) to exclude persons with prevalent disease. To capture disease cases emerging in the community setting, we limit ascertainment to those sites of care where incident presentation would be present and use only primary diagnoses of hospitalization, as secondary diagnoses often represent conditions emerging during hospitalization.

Confounders

In the present study, we expect complete information on the central confounders of age, sex, calendar year, country, and seasonality, as these are measured as key variables in the registers and information on these variables has to be entered into the system to establish a record file.

Information on the three confounders of severity of rhinitis, asthmatic status, and chronic urticaria status is challenging to obtain from the nationwide registers for many reasons. First of all, these conditions in general emerge in the primary health care sector where patients normally seek care from their general practitioner for treatment of symptoms. Second, truncation bias may, as with regard to the measures of exposure and outcome, also occur in relation to these three confounders in Norway as the patient register was established in 2008, making the follow-up period rather short. Third, different issues regarding codes and use of drugs for the three conditions have to be realized and discussed to understand the potential impact of residual confounders in the present study. We have discussed these issues with clinical experts and the essence of the discussion is given below.

- Severity of rhinitis is measured as use of immunotherapy and the binary measure of severity of rhinitis will not capture different levels of disease severity. Therefore, we expect the sensitivity of the measure to be rather low and severity of rhinitis to be underreported in the present study. However, we do not expect misclassification of those persons who received immunotherapy, as it is assumed that persons receiving immunotherapy also have severe rhinitis. A quantitative bias analysis examining the impact of misclassification of severity of rhinitis on the results will be performed.

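### In Substudies 3B and 4B, SVT or A-fib/flu first recorded after DL start as a secondary or outpatient diagnosis does not end follow-up, so a later primary admission can count as a 'first' event

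*Protocol*

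**What the plan says.** **Outcome.** Protocol 7.3.2 states "For all outcome variables, we will include the primary diagnoses from the emergency room or inpatient settings registered in the Nordic national patient registers". Section 7.9 gives the reason: the study will "use only primary diagnoses of hospitalization, as secondary diagnoses often represent conditions emerging during hospitalization".

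**Prevalent disease, 3B and 4B.** Section 7.2.2 removes anyone with a diagnosis of SVT or A-fib/flu ahead of DL use. It sets no limit on diagnostic position or care setting. Section 7.9 describes the principle: "To differentiate between incident and prevalent disease, we exclude persons with registered disease before baseline".

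**End of follow-up.** For 3B, section 7.7.3 states "Study individuals are followed until occurrence of a SVT; 31 December 2015; emigration; or death, whichever comes first". For 4B, section 7.7.4 states "Study individuals are followed until occurrence of A-fib/flu; 31 December 2015; emigration or death, whichever comes first". Substudy 2B differs. Section 7.7.2 states "Study individuals are followed until occurrence of a seizure; occurrence of one of the conditions described in section 7.2.2", before the administrative end date, emigration and death.

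**Descriptive substudies.** In 3A and 4A, section 7.2.2 excludes "Individuals with a diagnosis of SVT or A-fib/flu before entering the study period, as they have prevalent disease". In 2A, earlier seizure, epilepsy and antiepileptic use are also judged at entry to the study period. Tumour and trauma are judged up to the event: "Individuals with a diagnosis of malignant brain tumor or head trauma before the first seizure".

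**The concern.** The objectives in section 6 are about incident disease. In 3B and 4B the protocol applies a wide definition of disease to decide who is prevalent at baseline and a narrow one to decide who has an event. Nothing connects the two during follow-up. A-fib coded as a secondary diagnosis the day before the first DL dispensing makes a person prevalent. The same code the day after leaves that person at risk of a first A-fib, possibly for years.

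The timing is not neutral. Cohort entry is a dispensing date, so all follow-up begins exposed, and unexposed time cannot begin before week 26. Known but uncounted disease starts at zero and builds up, so later admissions from it fall disproportionately in reference time. In a safety study, a bias that raises the reference rate tends to hide harm.

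**Working it through.** **1. The rules side by side (3B, 4B)**

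| Step | Rule | Secondary or outpatient code recognised? |
|---|---|---|
| Baseline exclusion (7.2.2) | any diagnosis | yes |
| Outcome (7.3.2) | primary, emergency room or inpatient | no |
| End of follow-up (7.7.3, 7.7.4) | outcome, 31 December 2015, emigration, death | not stated |

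Example for 4B: DL starts in 2006, A-fib is coded as secondary in 2009, and a primary A-fib admission follows in 2012. Read literally, the person is at risk until 2012 and is a first case in that year.

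**2. A yardstick from the plan.** No stated figure is challenged here. Table 8 gives a minimum detectable IRR of 1.1 for A-fib at age 65 and over. Check by Annex 7: p2 = 1 - exp(-0.021543 × 6) = 0.121; E = 13.20/52 = 0.254; n = 44,500; one-sided 5%, power 80%. Solving gives 1.075, which agrees.

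**3. Illustrative size.**

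From the protocol: rate 2154.3 per 100,000 (Table 8), 6 years (7.5.4), unexposed from week 26 (7.3.1).

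Assumed: true IRR 1.5; 8-week exposed periods; 0.8 refills per year; a share s of new disease first recorded outside the outcome definition (30-50%); a yearly rate h of later primary admission in those people (5-15%).

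The cohort is moved forward week by week. D0 is disease-free and D1 is known but not yet counted.

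- New disease = D0 × (1 - exp(-0.021543 m/52)), with m = 1.5 when exposed and 1 otherwise. A fraction 1 - s is counted and a fraction s moves to D1.
- Later admissions = D1 × (1 - exp(-h k/52)). When exposed, k = 1 (no DL effect on later admissions) or k = 1.5 (same effect); otherwise k = 1.
- IRR = (exposed events / exposed time) / (unexposed events / unexposed time). Weeks 8-25 after a dispensing count in neither.

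| s | h per year | IRR, k = 1 | IRR, k = 1.5 | Recurrences among counted events (k = 1) | IRR if censored at first record |
|---|---|---|---|---|---|
| 30% | 5% | 1.460 | 1.485 | 6% | 1.500 |
| 30% | 15% | 1.400 | 1.457 | 13% | 1.500 |
| 50% | 5% | 1.410 | 1.465 | 12% | 1.500 |
| 50% | 15% | 1.303 | 1.414 | 26% | 1.500 |

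Person-level simulation under the same assumptions gave about 1.47-1.31 (k = 1) and 1.49-1.38 (k = 1.5). The two methods differ by at most about 0.03, which changes no conclusion.

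**4. Direction.** Two mechanisms act. One is dilution by admissions that DL does not affect. The other is timing, because recurrences come late. At a true IRR of 1.0 dilution does nothing, and timing alone gives 0.99-0.94 in this model. A separate model used 30-70% first recorded elsewhere, 0.05-0.20 later admissions per year, and either yearly dispensing or one early dispensing. There a null IRR read 0.91-0.99 or 0.51-0.96 respectively. Upward bias is also possible. With half of disease recorded elsewhere, 0.20 later admissions per year, yearly dispensing, age 65 and over, and DL raising later admissions two- to threefold, a true 1.3 read 1.42-1.66.

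**5. Substudy 2B.** The follow-up sentence points to the conditions in section 7.2.2. The first 2B bullet there names seizures, epilepsy and antiepileptic prescriptions, but as conditions preceding DL. The censoring bullet names brain tumour, antiepileptic initiation and head trauma, but not an epilepsy diagnosis. The two sections do not settle whether an epilepsy code, or a seizure code that does not qualify as an outcome, ends follow-up after DL start.

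**The case against.** **Table 2 defines an incident case by its first diagnosis.** On that reading the person coded in 2009 is not a first case in 2012, and such detail may be settled in the SAP, which was not examined here. The reading is available, but no section says that first means first in any position or setting, and 7.3.2 points the other way. Section 7.7 defers the specification of supplementary analyses to the SAP; the outcome definition and end of follow-up are set in the protocol. Even on the favourable reading, the protocol does not say when that person leaves the risk set.

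**Primary-only is a reasoned choice.** It is, and it should stay as the outcome definition. The reason concerns which records are counted. It does not explain why someone with recorded A-fib should remain at risk of a first A-fib.

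**The size depends on inputs outside the protocol.** This stands. The larger shifts need the further assumption that DL does not affect later admissions. With the same effect and the 2.30 prescriptions per year that section 7.5.2 gives for age 65 and over, the IRR is 1.49-1.45.

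**The descriptive substudies count only a first event, so a fixed date suffices.** That works for earlier qualifying events. It does not cover non-qualifying records made during the study period, which runs up to 15 years (Table 5). The consequence is smaller there, because person-years come from 1 January population counts and no exposure contrast is estimated.

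**Comparability with P203.** Section 5 says that removal of the secondary analyses is the only change in methods. A new main rule has a real cost, which the fix addresses.

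**Conclusion.** The gap is real in 3B and 4B on the literal text, and none of the listed supplementary analyses tests it. The likely direction is downward. Under the stated assumptions a true IRR of 1.5 would read about 1.47-1.31 if DL has no effect on later admissions and about 1.49-1.38 if it has the same effect, with roughly 6-26% of counted events being recurrences. The lower values are shifts larger than the distance from 1 to the IRR of 1.1 that Table 8 calls detectable at age 65 and over. The size remains illustrative: the shares, the later admission rate and the refill pattern are assumed, and only A-fib at that age was modelled.

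A reader might infer three stronger things that the protocol does not support:

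- **That 2B has the same gap.** It has an additional stop, and antiepileptic initiation expressly censors. The epilepsy code there is an ambiguity between two sections, not a plain omission.
- **That the IRR is always pulled toward 1.** A null IRR can fall below 1, and upward bias is possible if DL triggers admissions in known disease.
- **That the loss is quantified.** No figure in the protocol fixes it.

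**What to change.** 1. **3B and 4B:** apply the any-diagnosis rule during follow-up as well. Censor, without counting an event, at the first register record of the disease in any diagnostic position or setting that precedes a qualifying primary emergency-room or inpatient diagnosis. State in Table 2 what first means. If comparability with the P203 report must be kept, report the current rule alongside.
2. **2B:** reconcile sections 7.2.2 and 7.7.2 by stating whether an epilepsy diagnosis, or a seizure diagnosis that does not qualify as an outcome, ends follow-up after DL start.
3. **2A, 3A and 4A:** judge prior own-outcome disease (and epilepsy and antiepileptic use in 2A) before the first qualifying event, as 2A already does for tumour and head trauma.

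Cost: protocol and SAP wording and some programming. The sources appear to be in hand, since the Table 5 footnotes list outpatient contacts for Denmark, Finland and Sweden, and the asthma definition in Table 4 already uses secondary diagnoses. The downside is somewhat fewer events, some person-time lost to secondary codes, and a small departure from the three-country analysis.

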7.7.5 Supplementary analyses

The following supplementary analyses will be conducted. Unless otherwise specified, supplementary analyses will be performed on the total population (i.e. not stratified by age) and using the primary exposure definition.

(1) alternative definitions of exposure based on time since last DL dispensing (periods 0-4, 5-8, 9-16, and 17-26 weeks each compared with >26 week since last DL dispensing) for Substudies 2B, 3B, and 4B. Because as-needed medications, such as antihistamines may not be taken daily, this approach reflects the clinical expectation that the probability of actual exposure on a given day is highest shortly after filling a prescription and diminishes with increasing time. Each time a DL prescription is refilled, the time since last dispensing will reset to 0.

(2) for Substudy 2B, differentiating between febrile and non-febrile seizures for children aged 0–4 years.

(3) for Substudies 2B, 3B, and 4B, analyses will exclude persons who have been diagnosed with chronic urticaria and/or have redeemed very high doses of DL (dose for chronic urticaria is typically 4 times the standard dose for allergic rhinitis). To operationalize the exclusion of persons with chronic urticaria and/or who redeems high doses of DL, we will exclude person time at risk for a person from the date of a diagnosis of chronic urticaria or

date of DL prescription redemption of an amount of pills equal to at least twice the days' supply of DL for the individual's age in the period before next DL prescription redemption.

(4) the association analyses in Substudies 2B, 3B, and 4B will be stratified by countries to examine potential differences across countries.

(5) additional supplementary analyses, which will be specified in the SAP, will evaluate the potential effect of exposure misclassification in Substudies 2B, 3B, and 4B (i.e. evaluate use of loratadine and other non-sedating prescription antihistamines).

(6) a supplementary analysis for Substudies 2B, 3B, and 4B will evaluate whether the potential risk of the outcomes is higher following the first ever-DL prescription redemption compared to the second, third prescription redemption etc.

(7) a supplementary analysis for Substudies 2B, 3B, and 4B for which non-exposed periods start 52 weeks following the last prescription redemption.

(8) a supplementary analysis using an alternative adjustment set to examine the robustness of the study results. This adjustment set consists of age, sex, country, calendar year, seasonality, severity of rhinitis, asthmatic status, diabetes, hypo-/hyperthyroidism, inflammatory disease, infections, type 1 allergy. For the outcomes supraventricular tachycardia and atrial fibrillation or flutter, antihypertensive treatment will also be added.

(9) a supplementary analysis restricted to calendar time where misclassification due to over-the counter (OTC) use does not exist.

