We used the open source and freely available software DAGitty for the development of the DAGs [Textor, J., et al 2011]. DAGitty helps the researcher visualize the structure of relevant factors for the association under study included in the DAG, as well as to identify the minimum sufficient adjustment sets available for confounder adjustment to provide an unbiased estimate of the association of interest.

After the DAG meeting and discussions, the final directed paths that were drawn from each factor to the other factors in the DAGs were listed in the right column. Furthermore, we listed the different minimum sufficient adjustment sets identified by use of DAGitty for the three DAGs developed. We selected the final minimum sufficient adjustment set that will be used to adjust for confounding factors in the association studies based on whether we found that a given combination of confounders would be obtainable from the registers. Since there is no information on smoking or type 1 allergy available in the population registers, minimum sufficient adjustment sets including these two potential confounders were not eligible for selection. In cases where multiple minimum sufficient adjustment sets were candidates for confounder adjustment, we chose the minimum sufficient adjustment set where we found that the combination of confounders had the highest possible validity and quality in the population registers. Operational definitions of the variables in the minimum sufficient adjustment set are provided in the study protocol.

Afterwards, the DAGs were updated according to the final confirmed DAG meeting minutes and the final results were added to the protocol.

DAG for the association between DL use and seizure.

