Type 1 allergy	Type 1 allergy can affect risk of chronic urticaria and rhinitis. Seasonality affects risk of type 1 allergy.	There is a directed path from type 1 allergy to: Disease severity of rhinitis Asthmatic status Chronic urticaria

Figure 2 DAG for the association between DL use and first seizure

[figure not shown]

Table 11 Minimum sufficient adjustment sets for the DAG developed (Figure 2)

Potential confounders	Minimum sufficient adjustment sets																		
	1	2	3	4	5	6	7	8	9	10	11	12	13	14	15	16	17	18	19
Age	X	X	X	X	X	X	X	X	X	X	X	X	X	X	X	X	X	X	X
Sex	X	X	X	X	X	X	X	X	X	X	X	X	X	X	X		X		X
Country	X	X	X	X	X			X	X	X	X								
Calendar year	X	X	X	X	X	X	X	X	X	X	X	X	X	X	X				
Seasonality	X	X	X	X	X	X	X	X	X	X	X								
Disease severity of rhinitis	X	X	X	X	X	X		X	X	X	X								
Asthmatic status	X	X	X	X	X	X	X	X	X	X	X								
COPD	X	X	X	X															
Smoking						X	X					X	X	X	X	X	X	X	X
Metastatic disease																			
Drug overdose																			
Drug and alcohol abuse																X		X	
Diabetes	X	X						X	X				X			X	X		
Hypoglycemic agents																		X	X
Stroke		X		X					X		X				X	X	X	X	X
Chronic urticaria					X	X	X					X							
Thyroidism (hypo-/hyperthyroidism)	X	X						X	X				X						
Unspecific autoimmune disease			X	X						X	X			X	X				
Inflammatory disease	X		X					X		X			X	X					
Infections								X	X	X	X	X							
Type 1 allergy	X	X	X	X			X	X	X	X	X	X							

Light grey background = confounder information not available in population registers (e.g., self-reported lifestyle factors).

Dark grey background = selected minimum sufficient adjustment set (number 5) and the alternative set (number 8).

The minimum sufficient adjustment set chosen for analysis

[Table 11](#) shows the possible minimum sufficient sets available. The set used to adjust for confounding of the association between DL and seizures included the following confounders: age, sex, country, calendar year, disease severity of rhinitis, asthmatic status, and chronic urticaria. The selected set was chosen as it was the only one not including smoking and type 1 allergy.

Some rare diseases are treated with very high doses of desloratadine

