Unspecific autoimmune disease	
Unspecific autoimmune disease is associated with risk of chronic urticaria, thyroidism, and diabetes.
	
There is a directed path from unspecific autoimmune disease to:
 
Diabetes
 
Thyroidism
 
Chronic urticaria

Type 1 allergy	
Type 1 allergy can increase the risk of chronic urticaria and rhinitis.
 
Seasonality affects risk of type 1 allergy.
	
There is a directed path from type 1 allergy to:
 
Disease severity of rhinitis
 
Asthmatic status
 
Chronic urticaria

Antihypertensive treatment	
Hypertension affects the use of antihypertensive treatment.
 
Use of antihypertensive treatment increases the risk of chronic urticaria.
	
There is a directed path from antihypertensive treatment to:
 
Chronic urticaria

Figure 3 DAG for the association between DL use and A-fib/flu

[figure not shown]

Table 13 Minimum sufficient adjustment sets for the DAG developed (Figure 3)

Potential confounders	Minimum sufficient adjustment sets																	
	1	2	3	4	5	6	7	8	9	10	11	12	13	14	15	16	17	18
Age	X	X	X	X	X	X	X	X	X	X	X	X	X	X	X	X	X	X
Sex	X	X	X	X	X	X	X	X	X	X	X	X	X	X	X	X	X	X
Country	X	X						X			X	X						
Calendar year	X	X	X	X	X	X	X	X	X	X	X	X	X	X	X	X	X	X
Seasonality	X	X	X	X	X	X	X	X	X	X	X	X	X	X	X	X	X	X
Disease severity of rhinitis	X	X						X	X		X	X						
Asthmatic status	X	X	X	X			X	X	X	X	X	X	X	X				
COPD					X	X	X								X	X	X	X
Smoking			X	X	X	X			X	X			X	X	X	X	X	X
Inflammatory disease	X	X	X	X	X	X	X				X	X	X	X		X	X	X
Infections	X	X	X	X	X	X					X	X	X	X	X	X	X	X
Hypertension							X				X	X	X	X		X	X	X
Drug overdose																		
Drug and alcohol abuse																		
Thyroidism (hypo-/hyperthyroidism)	X		X		X		X				X		X			X	X	
Diabetes	X		X		X		X				X		X			X	X	
Structural heart disease							X											X
Stroke																		
Chronic urticaria							X	X	X	X					X			
Unspecific autoimmune disease		X		X		X						X		X				X
Type 1 allergy	X	X					X			X	X	X			X			
Antihypertensive treatment	X	X	X	X	X	X												

Light grey background = confounder information not available in population registers (e.g., self-reported lifestyle factors).

Dark grey background = selected minimum sufficient adjustment set (number 8) and the alternative set (number 1).

The minimum sufficient adjustment set chosen for analysis

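### Supplementary analysis 8 adjusts for type 1 allergy, which Annex 8 says the registers do not hold; if it is simply dropped, the set is no longer sufficient under the protocol's own DAGs

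*Protocol*

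**What the plan says.** Section 7.7.5, item 8, plans an analysis with an alternative adjustment set to test robustness. The set keeps age, sex, country, calendar year, seasonality and severity of rhinitis, and continues with "asthmatic status, diabetes, hypo-/hyperthyroidism, inflammatory disease, infections, type 1 allergy". For SVT and A-fib/flu, "antihypertensive treatment will also be added". Chronic urticaria, which is in the primary set, is not in this list.

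Annex 8 (12.8) explains how sets were chosen. It states that "there is no information on smoking or type 1 allergy available in the population registers" and that "minimum sufficient adjustment sets including these two potential confounders were not eligible for selection". For seizures it applies the rule again: "The selected set was chosen as it was the only one not including smoking and type 1 allergy".

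The footnotes to the set tables nevertheless mark alternative sets. Table 11 (seizures) has "selected minimum sufficient adjustment set (number 5) and the alternative set (number 8"; Table 13 (A-fib/flu) has "selected minimum sufficient adjustment set (number 8) and the alternative set (number 1"; Table 14 (SVT) marks number 9 as selected and number 3 as the alternative. Section 7.4.1 makes existing national register data the only data source.

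**The concern.** One variable is treated in two incompatible ways. It disqualifies a set from being primary because it cannot be measured, and it is then a required covariate in the robustness set drawn from the same registers.

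What is at stake is the one planned analysis that changes the covariate set. An analyst who finds no such variable may well run the list without it. The listed sets are minimum sufficient sets, so removing a member is not harmless. A difference from the primary result could then come from a newly opened path, and agreement would reassure less than it appears to.

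**Working it through.** No arithmetic applies; the check is of consistency and of graph structure.

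**1. Do the lists match?** The list in 7.7.5 item 8 equals set 8 of Table 11. With antihypertensive treatment added it equals set 1 of Table 13 and set 3 of Table 14. All three contain type 1 allergy and omit chronic urticaria and smoking. By the Annex 8 eligibility rule, none could have been selected.

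**2. Is the set sufficient, with and without type 1 allergy?** The three graphs were rebuilt from the directed paths in Table 10 (seizures) and Table 12 (A-fib/flu), with the SVT changes described in Annex 8. The back-door criterion was tested by d-separation. The primary set was taken with seasonality, as in Table 3 and sections 7.7.2 to 7.7.4.

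| Set | Seizures | A-fib/flu | SVT |
|---|---|---|---|
| Primary set | sufficient | sufficient | sufficient |
| Alternative set, with type 1 allergy | sufficient | sufficient | sufficient |
| Alternative set, without type 1 allergy | not sufficient | not sufficient | not sufficient |
| Alternative set, without type 1 allergy, with chronic urticaria | sufficient | sufficient | sufficient |

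The first two rows reproduce the protocol's own statement that the primary and alternative sets are sufficient.

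**3. Why the third row fails.** The open path for seizures is:

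DL <- chronic urticaria <- type 1 allergy -> [asthmatic status] <- smoking -> seizures

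- Chronic urticaria lies on the path and is not adjusted for, so it does not block.
- Type 1 allergy is a common cause of chronic urticaria and asthmatic status; once dropped, it does not block.
- Asthmatic status is a common effect of type 1 allergy and smoking. It is adjusted for, which opens the path.
- Smoking has no register data and is in neither set.

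The primary set closes this path at chronic urticaria, and the full alternative set closes it at type 1 allergy. For A-fib/flu the path continues from smoking through COPD, hypertension or structural heart disease; for SVT, through structural heart disease or stroke.

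**4. Do defects in the tables change this?** The arrows in Table 12 contain a cycle: inflammatory disease -> structural heart disease -> pre-stroke -> inflammatory disease. Dropping each of the three arrows in turn left the first three rows unchanged for A-fib/flu and SVT. Table 3 lists thyroidism, inflammatory disease and infections as absent from the seizure DAG, whereas Table 10 includes them. None of these lies on the open seizure path, so that path stays open on either reading.

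**5. Which listed sets avoid both smoking and type 1 allergy?**

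- Table 11 (seizures): only set 5, the primary set, as the protocol says.
- Table 13 (A-fib/flu): only set 8, the primary set.
- Table 14 (SVT): set 9 (primary) and set 17 (age, sex, infections, thyroidism, structural heart disease, stroke). Set 17 also tested sufficient.

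Outside the listed sets, the A-fib/flu alternative without type 1 allergy becomes sufficient if COPD, hypertension and structural heart disease are added.

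**The case against.** The best defence is that section 7.7 leaves the specification of supplementary analyses to the SAP, which is not at hand. The SAP may define a register proxy for type 1 allergy, as the protocol uses immunotherapy as a proxy for severe rhinitis. The lack of an allergy code in Annex 6 proves nothing: Annex 6 has no codes for diabetes, thyroid disease, inflammatory disease, infections or antihypertensive treatment either. Nor does the protocol say that type 1 allergy will be dropped, so the insufficiency is conditional on that step. All of this stands. It does not remove the contradiction: the covariate list is fixed in the protocol, and a proxy would itself conflict with the Annex 8 statement, which would need correcting.

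Three stronger readings are tempting and not supported:

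- **That all checks on confounding rest on analysis 8.** Section 7.9 plans quantitative bias analyses for misclassified rhinitis severity, asthma and chronic urticaria, and supplementary analysis 3 excludes person-time linked to chronic urticaria or high-dose redemption. Analysis 8 is only the sole analysis with a different covariate set.
- **That its result would be worthless.** An open path shows that bias is possible. The documents give no strength for any arrow on it, so the bias may be small.
- **That the main results are confounded for this reason.** The primary sets were sufficient in every version of the graphs tested.

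A fair criticism of the remedy is that it restores chronic urticaria, whose sensitivity section 7.9 expects to be somewhat low, and so loses a check that does without that variable. This also stands and is carried into the fix.

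**Conclusion.** The point holds as a contradiction between section 7.7.5 item 8 and Annex 8, with a conditional consequence. Analysis 8 cannot be built as written from the data the protocol describes. If type 1 allergy is left out without a proxy, the remaining set is insufficient for all three outcomes under the protocol's own arrows.

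The reach is one supplementary analysis; the primary analyses of Substudies 2B, 3B and 4B are unaffected. The size of any bias cannot be computed from the documents. The graph result assumes that the arrows in Tables 10 and 12 and the SVT changes are the intended DAGs, since Figures 2 to 4 are not shown. This should be corrected before analysis, but it does not threaten the study's main conclusions.

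**What to change.** Reconcile section 7.7.5 item 8 with Annex 8 in one of two ways.

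- **If a usable register proxy for type 1 allergy exists:** define it and correct the Annex 8 statements on availability and eligibility.
- **If not:** remove type 1 allergy and redefine analysis 8 as an extended set. This is the primary set, including chronic urticaria and seasonality, plus diabetes, hypo-/hyperthyroidism, inflammatory disease and infections, plus antihypertensive treatment for SVT and A-fib/flu. It is sufficient for all three outcomes (last row of the table above).

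The second option costs one sentence in 7.7.5 and edits to the footnotes of Tables 11, 13 and 14. Every added covariate is already planned for this analysis.

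State its limit: the extended set contains the whole primary set, so it tests the effect of adding covariates and is not an independent alternative. For seizures no other listed set is available. For SVT, set 17 of Table 14 could be run as an independent check. For A-fib/flu, the alternative set without type 1 allergy plus COPD, hypertension and structural heart disease would serve. Both assume that the extra variables can be obtained from the registers, and both need definitions for them.
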